Two to four weeks later, the participant will return to complete the second half of the study in which they are given the dose of U500 they did not get at the time of their previous visit. Between visits, subjects will be instructed to go back on their usual diabetes regimen. They will again be instructed to avoid exercise 48 hours before the study and provided with directions for how to manage their diabetes medications in the days immediately before the second visit. These will again be individualized based on the participant's current regimen with the intention to discontinue all medications so none are present at the start of the study. They will again report to the research center after dinner between 8-10 pm and maintained on an insulin drip as necessary to maintain blood glucose between 100-150 mg/dL. At 7 am on the next day the U500 dose will be given and samples will be collected as during the first visit. A glucose infusion will again be given to maintain euglycemia (100 mg/dL) and discontinued using the same plan as for the first visit.

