### *What is our study population?*

We will study adults with type 2 diabetes and insulin resistance. Criteria for participation are listed below.

- **Inclusion Criteria**
  - Type 2 diabetes
  - Ages 30-65 years
  - A1c between 7-9.5% within the past month
  - On  $\geq$ 100 units of insulin per day.

- Willing to discontinue oral/injectable non-insulin or insulin hypoglycemic agents for minimum of 15 hours prior to the expected U-500 dose administration.
- Willing to avoid exercise 48 hours prior to study
- Willing to be fasting for up to 24 hours
- BMI between 27 and 38 kg/m^2
- **Exclusion criteria**
  - On systemic corticosteroids in preceding 3 months
  - Heavy alcohol consumption (>21 drinks/week men, >14 drinks/week women)
  - Unwillingness to stop alcohol consumption for 24 hours before each study visit
  - Pregnant or actively trying to conceive
  - Current diagnosis of active infection, cancer (other than basal cell carcinoma), vascular disease, organ failure
  - Current transplant recipient

*How are subjects being selected into the study?*

Potential participants will be recruited from the Diabetes Clinics at the University of Minnesota. They will initially be ascertained for eligibility by review of the electronic medical record or on referral by their personal health care provider.

*What are your treatment groups?*

Each individual will be studied twice, once after the administration of 100 units of U 500 and once after the administration of 200 units of U500. Dosage administration will be in random order.

*What is our assignment strategy?*

The investigational pharmacy at the University of Minnesota will dispense the doses of U 500 insulin and assign the order of administration based on a randomization scheme developed by [name], the biostatistician on the project.

*How many subjects per treatment group?*

We have powered the primary research question using 15 participants, each studied twice as described above. A participant who completes the first dose study but does not return for the second dose study will be replaced.

With 15 subjects (N = 15) completing this cross over study design, we have 85% power using a paired t-test to detect at least a 2 hour difference in the mean duration of action of the 100 vs 200 unit dose of U500 conservatively assuming a within-person correlation of 0.30 (Figure 2). Power will be higher (the detectable difference will be smaller) if the within-person correlation is larger.

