- **Sample size computation and power analysis**

We have powered the primary research question using 15 participants, each studied twice as described above. A participant who completes the first dose study but does not return for the second dose study will be replaced. With 15 subjects (N = 15) completing this cross over study design, we have 85% power using a paired t-test to detect at least a 2 hour difference in the mean duration of action of the 100 vs 200 unit dose of U500 conservatively assuming a within-person correlation of 0.30 (Figure 2).

- **Statistical analysis plan**

The duration (in hours) of 20 % dextrose infusion requirement, peak 20 % dextrose requirement , and the AUC of 20 % dextrose will be calculated for each subject after the administration of each of the 100 unit and 200 unit doses of U-500 regular insulin. These measures will then each be compared between doses by paired t-test.

- **Publication strategy**

We intend to submit a report of this work to Diabetes Care and submit an abstract to American Diabetes Association Scientific Sessions in 2015.

- **References**

1. Gagnon-Auger M, du Souich P, Baillargeon JP, Martin E, Brassard P, Menard J, Ardilouze JL. Dose-dependent delay of the hypoglycemic effect of short-acting insulin analogs in obese subjects with type 2 diabetes: a pharmacokinetic and pharmacodynamics study. *Diabetes Care*. 2010 Dec;33(12):2502-7.
2. Dailey AM, Williams S, Taneja D, Tannock LR. Clinical efficacy and patient satisfaction with U-500 insulin

use. *Diabetes Res Clin Pract.* 2010 Jun;88(3):259-64.

- de la Pena A, Riddle M, Morrow LA, Jiang HH, Linnebjerg H, Scott A, Win KM, Hompesch M, Mace KF, Jacobson JG, Jackson JA. Pharmacokinetics and pharmacodynamics of high-dose human regular U-500 insulin versus human regular U-100 insulin in healthy obese subjects. *Diabetes Care.* 2011 Dec;34(12):2496-501.

Figure 1: Study Design

[figure not shown]
[figure not shown]

Figure 2: Power to detect a within-person difference in mean duration of action (hours) for dose 100 units vs. dose 200 units of U500 insulin. Type I error 5% assumed.

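### The paired t-test ignores visit order: it stays valid, but a visit effect of about 1 h or more would cost power that a period-adjusted analysis with balanced sequences keeps for about 0.6 points

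*Combined protocol and SAP*

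**What the plan says.** All passages are in the combined protocol and SAP.

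- **Design.** Under What are your treatment groups?, each participant receives both doses: "Dosage administration will be in random order". How will we do the work? sets the interval: "Two to four weeks later, the participant will return to complete the second half of the study".
- **Allocation.** Under What is our assignment strategy?, the investigational pharmacy will "assign the order of administration based on a randomization scheme developed by" the project biostatistician. The text does not say whether the scheme is blocked or balances the two sequences.
- **Replacement.** How many subjects per treatment group? states: "A participant who completes the first dose study but does not return for the second dose study will be replaced". It does not say which sequence the replacement receives.
- **Power.** Sample size computation and power analysis states: "We have powered the primary research question using 15 participants, each studied twice as described above", and "we have 85% power using a paired t-test to detect at least a 2 hour difference in the mean duration of action", with a within-person correlation of 0.30. The Figure 2 caption adds "Type I error 5% assumed".
- **Analysis.** The Statistical analysis plan section defines the three measures and then gives the whole comparison in one sentence: "These measures will then each be compared between doses by paired t-test". No period, visit or sequence term appears anywhere in the protocol.

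**The concern.** Randomising the order stops a visit effect from favouring either dose on average, but it does not take that effect out of the error variance. Let p be the additive effect of visit 2 minus visit 1. The 200 minus 100 unit difference is raised by p in people who receive 100 units first and lowered by p in the others. The paired t-test treats that spread as random error, so its confidence interval widens and its power falls. The stated 85% therefore holds only if p = 0.

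There is also a conditional effect. Fifteen completers cannot divide equally between two sequences. Given the split that occurs, the estimate is shifted by p times the imbalance divided by 15. This is trivial at 8/7 but not at 11/4, and the text neither predicts nor excludes a lopsided split. With 15 people there is little margin to absorb either effect. The sequence is assigned by the pharmacy and already known, so using it needs no new data.

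**Working it through.** **Inputs from the documents.** N = 15 completers; difference 2 h; power 85%; paired t-test; type I error 5%; correlation 0.30.

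**Assumptions.** The test is two-sided (the available text does not say). The SD is not in the available text, since Figure 2 is not shown, so 85% cannot be checked independently and is used to find the SD. The visit effect p is not given and is varied from -2 to +2 h.

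**Step 1: SD implied by the plan's 85%.** Noncentrality = 2 × √15 / SD with 14 df. Power of 85% requires SD of differences = 2.40 h, so noncentrality = 7.746 / 2.403 = 3.22. At correlation 0.30 the SD per dose is 2.403 / √(2 × 0.70) = 2.03 h.

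**Step 2: effect of p on the paired t-test.** Let n1 be the number given 100 units first and n2 = 15 - n1.
- Shift of the estimate = p(n1 - n2)/15. At 8/7 this is p/15, or 4 minutes per hour of p.
- Expected sample variance of the differences = SD² + p² × 4·n1·n2/(15 × 14). At 8/7 and |p| = 1 h: 5.77 + 1.07 = 6.84. At |p| = 2 h: 5.77 + 4.27 = 10.04.

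**Step 3: the period-adjusted analysis.** Its estimate is the plain average of the two sequence means, [(d + p) + (d - p)]/2 = d, so p cancels. SE = (SD/2) × √(1/n1 + 1/n2) with 13 df. At 8/7: 1.201 × √(1/8 + 1/7) = 0.622 h, noncentrality 2/0.622 = 3.22, power 84.4%.

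**Step 4: results at 8/7, true difference 2 h** (simulation, at least 200,000 trials per cell):

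| p (h) | Paired-t power (+p / -p) | Adjusted power | Paired-t type I error |
|---|---|---|---|
| 0 | 85.0% | 84.4% | 5.0% |
| ±0.5 | 85% / 83% | 84.4% | 4.6% |
| ±1 | 83% / 78% | 84.4% | 3.6% |
| ±2 | 72% / 58% | 84.4% | 1.3% |

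Mean 95% CI width, paired against adjusted, is 2.85 against 2.63 h at |p| = 1 h, and 3.46 against 2.63 h at 2 h.

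**Step 5: simple 1:1 randomisation instead of a fixed 8/7.** Paired-t power is 85.0%, 83.5%, 79.0% and 63.0% at |p| = 0, 0.5, 1 and 2 h. Type I error is 5.0-5.1% and mean bias 0.00 h. Adjusted power averages 81.8%.

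**Step 6: dependence on the realised split:**

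| Split | Adjusted power | Shift of paired estimate per hour of p | Paired-t type I error at \|p\| = 1 h |
|---|---|---|---|
| 8/7 | 84.4% | 1/15 h = 4 min | 3.6% |
| 9/6 | 83.1% | 3/15 h = 12 min | 4.3% |
| 10/5 | 80.2% | 5/15 h = 20 min | 6.0% |
| 11/4 | 75.1% | 7/15 h = 28 min | 8.6% |

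If simple randomisation were used, a split of 10/5 or worse would occur with probability 2 × 4944/32768 = 30%.

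**Step 7: other SDs.** For SD per dose from 1.5 to 3.0 h, the cost of adjusting at 8/7 with no visit effect runs from 0.2 to 0.7 points (for example 98.2% to 98.0% at 1.5 h, 68.3% to 67.6% at 2.5 h).

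**The case against.** The strongest reply is that nothing is wrong. The paired t-test is valid over the randomisation and conservative at 8/7, and no document shows a visit effect. The protocol repeats the same conditions at both visits, two to four weeks apart and double blind, which limits the likely sources of one. A 1 h shift is half the target difference and a 2 h shift is all of it. This stands, and it is why the point is put as protection rather than correction. It does not show that p is zero, and the analysis has to be fixed before results are seen.

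The gain can also be small or absent. At 8/7 it is about 1.4 points at p = +1 h. At +0.5 h the paired test is slightly ahead (85.1% against 84.4%). The larger loss needs the opposite sign, which nothing predicts. This stands too: 1 h is roughly where the average loss becomes material, not a threshold.

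The 0.6-point price depends on balance. If allocation were simple and only the period term were added, average power would be about 82% and the two methods would break even near |p| = 0.75 h. That is right, and it means the two changes belong together. The biostatistician's scheme may already be blocked; if so, it only needs stating.

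Finally, the SD is back-solved. If the correlation were 0.50 with the same SD per dose, the paired test would have about 94% power, and 89% at |p| = 1 h under simple randomisation. The loss would then still leave power above the planned 85%. That is a fair limit on the consequences, but 0.30 is the value the plan chose. The magnitudes here concern duration only; for peak and AUC the reasoning carries over but no size has been calculated.

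**Conclusion.** The point holds as a worthwhile, low-cost improvement. The planned test is valid but leaves power exposed to any visit effect. Averaged over the sign of the effect at 8/7, power falls from 85% to about 80% at 1 h and about 65% at 2 h. Averaged over simple randomisation it falls to 79% and 63%. The adjusted analysis at 8/7 stays at 84.4% throughout. Type I error above 5% arises only conditionally on a lopsided split of about 10/5 or worse.

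These figures rest on an SD of differences of 2.40 h implied by the plan's own power claim, a two-sided 5% test, a true difference of 2 h, and an additive visit effect of assumed size. The hour values scale with the SD.

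**What to change.** Make two changes together.

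1. **Statistical analysis plan section.** For duration, peak and AUC, replace the paired t-test with a crossover model containing dose, period and sequence, with participant as a random effect. For complete pairs this is the same as comparing within-person visit differences between the two sequences by a two-sample t-test (Hills-Armitage).
2. **Assignment strategy section.** State that the randomisation is blocked to give 8/7 among completers, and that each replacement is assigned the sequence of the person replaced.

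The cost is SAP wording, one line in the randomisation scheme and one degree of freedom. With no visit effect, power falls from 85.0% to 84.4% at 8/7. Without the balance requirement the cost is larger: about 3 points on average under simple randomisation, and about 10 points at 11/4 (85.0% - 75.1%). No extra data, visits or participants are needed. A period term does not deal with carry-over, and the text should not claim that it does.

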## U-500 Insulin Safety Plan

**Situation:** Non-standard insulin concentrations (eg. U-500) are high risk medications that require additional safety measures to prevent errors.

**Background:** Insulin products are typically prescribed using a concentration of U-100 (100 units/mL). Increasingly we are seeing requests for non-standard concentrations, particularly for the commercially available U-500 (500 units/mL) regular insulin. This product can be difficult to order, prepare and administer. An error with this high risk medication could have significant adverse events associated with the administration and result in severe, prolonged hypoglycemia.

U-500 regular insulin is typically used in patients that have a high resistance to insulin, most often in patient that require >100 units/dose. This insulin is usually administered on a q8h schedule (NOT PRN).

In the outpatient setting, patients are thought to use an insulin syringe to draw doses. Because of this, the nomenclature patients learn are usually both the actual dose of insulin they are to administer in actual units of insulin, as well as what mark on an insulin syringe to draw the dose up to. Example: 100 units of U-500 insulin = 20 units on an insulin syringe. This can be very confusing not only to patients, but to others providing care.

Our current safety practices for U-500 insulin:

Specific entry in Epic for U-500. Currently this requires both the actual Units of U-500 to be administered as well as the volume in mL to which it is to be drawn.

Storage in central pharmacy is in the C-II safe, away from all other insulin products  
Pharmacy must draw up individual doses

**Assessment:** Several aspects of our safety plan could be improved in addition to our current practices. These include:

### Formulary

- o Restrict to use only when each dose is >100 units
- o Implement pharmacy consult for **all** U-500 patients
  - Double check patient's home dose and make sure ordered correctly
  - Autosub any doses </= 100 units to regular U-100 insulin

### Ordering

- o BPA to fire for providers if dose is <101 units not allowing them to process order
- 0 . o Revise Epic ordering so that mLs is not part of the order as it leads to confusion because insulin syringe is not in mL
- 0 . o Attach a document to the order with a crosswalk of actual dose to units on an insulin syringe

### Storage/Preparation

- o All sites to draw to dose and store product in central pharmacy C-II safe
- 0 . o Require a pharmacy double check (best with 2 pharmacist, but if not available pharmacist/technician)

**Education**

- Reminder to Pharmacy and nursing staff

**Plan:** Approve above plan at 10/31/12 meeting. Get formulary approval for restrictions. Roll-out/educate other recommendations by 12/1/12.

May 2008 Formulary  
Committee Meeting

## **U-500 Regular Insulin**

**Situation:**

On occasion, a patient requiring very high doses of regular insulin will be prescribed U-500 regular insulin.

**Background:**

Regular insulin comes in two concentrations U-100 (100 units/mL) and U-500 (500 units/mL). Historically, Fairview has elected to not use the U-500 insulin because of potential errors that could result if this insulin was administered the U-500 in place of U-100 insulin, but in recent months we have had a few patients that warranted the use of U-500 due to doses in excess of 100 units..

To prevent accidental selection of this medication in both FCIS and WORx, the U-500 insulin was not included in the programming. Because of this a miscellaneous medication entry is required into the electronic system. When this feature is used, no alerts and safety features are built into the programming.

**Assessment:**

Because of the need to use this concentration on rare occasion, safety plans should be put into place to prevent errors.

**Recommendation:**

0. • Restrict prescribing of U-500 insulin to endocrinology
0. • Require the medication be stored in a separate location in central pharmacy (Whenever possible in the C-II safe fridge)
0. • Require all doses be drawn-to-dose (in an insulin syringe, with no overfill) in central pharmacy
1. • Add an alert in WORx stating the above
0. • On the insulin product page in FCIS, add this U-500 insulin to the non-formulary section with a note that it is restricted to endocrinology. If possible to create an MLM if U-500 insulin is ordered and the dose is <100 units/dose prohibiting use of U-500.
0. • Add teaching aid for nursing to FCIS in background

## **Regular Insulin U-500 Dosing Guidelines, Acute Care Diabetes Advisory Committee**

**Indication:** U-500 insulin shall be considered when a patient is on a total daily dose (TDD)

of insulin  $\geq$  250 units.

**Dosing:** Prescribe in ml and insulin unit equivalents on a U-100 Lo Dose  $\frac{1}{2}$  CC insulin syringe

U-500: 1ml = 500 units

0.1ml of U-500 = 50 units of U-100

Start at 0.1ml every 8 hours, which provides 150 units/ 24 hours Increase in increments of 0.05 ml in hospitalized patient every 1-2 days.

**Write as:**

U-500 Regular Insulin 0.1ml = 50 insulin unit equivalents

To draw this up in a U-100 insulin syringe, draw to 10 units on the insulin syringe. Frequency: Every 8 hours 0800-1600-0000 or 0700-1500-2300

Do Not Order Prandial Bolus Doses with this insulin.

You may utilize U-100 Regular Insulin High Resistance Correction scale if necessary. We typically do not.

1

## Conversion Information for Humulin® R U-500 (Concentrated) Insulin Dose

Humulin R U-500 dose (units)	U-100 insulin syringe (unit markings)	Volumetric (tuberculin or allergy) syringe volume (mL)
25	5	0.05
50	10	0.1
75	15	0.15
100	20	0.2
125	25	0.25
150	30	0.3
175	35	0.35
200	40	0.4
225	45	0.45
250	50	0.5
275	55	0.55
300	60	0.6
325	65	0.65
350	70	0.7
375	75	0.75
400	80	0.8
425	85	0.85
450	90	0.9
475	95	0.95
500	100	1.0

### Dosing Formulas U-100

#### insulin syringe

Divide prescribed dose (actual units of Humulin R U-500) by 5 = unit markings in a U-100 insulin syringe

#### Volumetric (tuberculin or allergy) syringe

Divide prescribed dose (actual units of Humulin R U-500) by 500 = volume (mL) in a volumetric syringe

## Indication for Humulin R U-500

- Humulin R U-500 is indicated as an adjunct to diet and exercise to improve glycemic control in adults and children with type 1 and type 2 diabetes mellitus.

- 0. • Humulin R U-500 is useful for the treatment of insulin-resistant patients with diabetes requiring daily doses of more than 200 units, since a large dose may be administered subcutaneously in a reasonable volume.

## Select Safety Information for Humulin R U-500

- 0. • Humulin R U-500 is contraindicated during episodes of hypoglycemia and in patients hypersensitive to Humulin R U-500 or any of its excipients.
- 0. • Starting or changing insulin therapy should be done cautiously and only under medical supervision.
- 0. • Humulin R U-500 contains 500 units of insulin in each milliliter (5 times more concentrated than Humulin R U-100). For Humulin R U-500, extreme caution must be observed in the measurement of dosage because inadvertent overdose may result in serious adverse reaction or life-threatening hypoglycemia.
- Fluid retention and heart failure can occur with concomitant use of TZDs and Humulin R U-500.

**Please see Important Safety Information starting on page 2 and accompanying Patient Information and Full Prescribing Information.**

2

## Important Safety Information for Humulin R U-500 (regular U-500 [Concentrated] insulin human injection, USP [rDNA origin])

### Contraindications

- 0. • Humulin® R U-500 is contraindicated during episodes of hypoglycemia and in patients hypersensitive to Humulin R U-500 or any of its excipients.

### Warnings

- 0. • Starting or changing insulin therapy should be done cautiously and only under medical supervision.
- 0. • Humulin R U-500 contains 500 units of insulin in each milliliter (5 times more concentrated than Humulin R U-100). For Humulin R U-500, extreme caution must be observed in the measurement of dosage because inadvertent overdose may result in serious adverse reaction or life-threatening hypoglycemia.
- 0. • Fluid Retention and Heart Failure with Concomitant Use of PPAR-gamma Agonists: Thiazolidinediones (TZDs), which are PPAR-gamma agonists, can cause dose-related fluid retention, particularly when used in combination with insulin, including Humulin R U-500. Fluid retention may lead to or exacerbate heart failure. Observe patients for signs and symptoms of heart failure and consider discontinuation or dose reduction of the PPAR-gamma agonist.

### Precautions

- Dosing Confusion/Dosing Errors: Medication errors associated with Humulin R U-500 have occurred and resulted in hyperglycemia, hypoglycemia, or death. The majority of errors occurred due to errors in dispensing, prescribing, or administration.
  - The Humulin R U-500 vial, which contains 20 mL, versus the Humulin R U-100 vial, which contains 10 mL, is marked with a band of diagonal brown stripes to distinguish it from the U-100 vial, which has no stripes. "U-500" is also highlighted in red on the label.
  - The prescribed dose of Humulin R U-500 should always be expressed in actual units of Humulin R U-500 along with corresponding markings on the syringe the patient is using (ie, a U-100 insulin syringe or volumetric [tuberculin or allergy] syringe).
  - A majority of administration errors occurred due to dosing confusion when the Humulin R U-500 dose was prescribed in units or volume corresponding to a U-100 insulin syringe or volumetric syringe markings, respectively, or the prescribed dose was administered without recognizing that the markings on the syringe used do not directly correspond to U-500 dose. Instructions for use should always be read

and followed before use.

- Instruct the patient to inform hospital or emergency department staff of the dose of Humulin R U-500 prescribed.
- A conversion chart should always be used when administering Humulin R U-500 doses with U-100 insulin syringes or volumetric syringes.
- **Hypoglycemia:** Hypoglycemia is the most common adverse reaction of all insulin therapies, including Humulin R U-500. Hypoglycemia may occur suddenly. Severe hypoglycemia may lead to unconsciousness, convulsions, temporary or permanent impairment of brain function, or death. As with all insulin preparations, the time course of Humulin R U-500 action may vary in different individuals or at different times in the same individual and is dependent on dose, site of injection, blood supply, temperature, and physical activity.
  - Adjustment of dosage of any insulin may be necessary in patients with renal or hepatic impairment or if patients change their physical activity or their usual meal plan, or during times of illness, emotional disturbances, or other stresses. Concomitant oral antidiabetic treatment may need to be adjusted; however concomitant use is not recommended.
  - Any patient who requires Humulin R U-500 for control of diabetes should be under close observation until appropriate dosage is established. Insulin resistance may be transitory, and dosage requirements may change over time. Use caution in patients with hypoglycemia unawareness and in patients who may be predisposed to hypoglycemia. The patient's ability to concentrate and react may be impaired as a result of hypoglycemia. These abilities are especially important in driving or operating other machinery.

Please see Important Safety Information continued on page 3 and accompanying Patient Information and Full Prescribing Information.	Continued on next page >
---	------------------------------------

3

